3.0 PATIENT SELECTION

3.1 Eligibility Criteria

1. Histologically or cytologically confirmed prostate cancer
2. Evidence of castrate testosterone level <50ng/dL (or surgical castration)
3. For Phase I portion of the study: Evidence of disease progression:
 - 2 or more new lesions on bone scan or
 - Progressive disease on CT/MRI according to RECIST 1.1 criteria⁴⁵ or
 - Rising PSA: PSA evidence for progressive prostate cancer consists of a minimum PSA level of at least 2 ng/ml, which has subsequently risen on at least 2 successive occasions, at least 2 weeks apart.
4. For Phase II portion of the study:

- Subjects must be on enzalutamide for metastatic CRPC and within the first 12 weeks of enzalutamide at 160mg/day
- Record of subject's enzalutamide start date and baseline PSA (within 28 days of starting) before starting enzalutamide available

5. Subjects must have documented clinically stable disease or better during the screening period of the study (see Section 7.1) as defined by all of the following (for Phase II portion of the study):

- PSA \leq 1.25 times the PSA at start of enzalutamide
- Lack of radiographic progression as defined by RECIST 1.1 and Prostate Cancer Working Group Criteria⁴⁴⁻⁴⁶
- Clinically stable as confirmed by treating physician

6. Any prior therapy for castrate disease is acceptable except prior specific CYP17 antagonists (e.g. abiraterone acetate, orteronel) or prior second generation AR antagonists (e.g. enzalutamide or ARN509) which are excluded other than enzalutamide as specified for phase II portion. A minimum washout of 28 days for any other anticancer therapy prior to first dose of study drug is required (only applicable for phase I).

7. Any other radiotherapy or radionuclide require 28-day washout prior to first dose of study drug.

8. Denosumab or zoledronic acid are allowed.

9. ECOG performance status \leq 2 (Appendix A).

10. Patients must have normal hepatic function as defined below:

• Total bilirubin	\leq 1.5 x the upper limit of normal
• AST(SGOT)/ALT(SGPT)	\leq 2.5 X institutional upper limit of normal

11. Ability to understand and the willingness to sign a written informed consent document.

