13.0 STATISTICAL CONSIDERATIONS

13.1 Sample Size/Primary Endpoint

Within the phase I portion of the study, steady-state C_{trough} for Enzalutamide and the active metabolite will be determined for each patient and means and standard deviations calculated. As described above, the mean of the ratio of C_{trough} for Enzalutamide and the active metabolite will be calculated for each dosing cohort, and mean value will be used for dos adjustment determinations. Standard deviation and range of the C_{trough} and ratio will also be calculated and reported.

The randomized phase II study, will be conducted with appropriate sample size to power primary endpoint- to determine if mifepristone in combination with enzalutamide prolongs time to PSA progression compared to enzalutamide alone in patients with metastatic castration resistant prostate cancer. The primary statistical consideration will be PSA progression-free survival (PFS) post randomization, defined as the time to PSA progression or death, whichever comes first. PSA progression will be defined as a PSA (confirmed 2 weeks later) that is ≥ 1.25 times (25% increase) the PSA at randomization (week 12). We assume the median time to PSA progression in the control (enzalutamide alone) arm will be 6 months post randomization. The rationale for this assumption is as follows. In the phase III enzalutamide (AFFIRM) trial¹³, ~10% of treated patients had PSA progression prior to 12 weeks. The PSA progression-free rate was ~42% at 9 months, which would correspond to a 6-month rate, conditional on no event at 12 weeks, of $0.42/0.9=0.47$. Thus our enrichment strategy should lead to a patient population with a median PFS of 6 months (24 weeks) in the control arm post randomization. In order to detect a hazard ratio (HR) of 0.60, which corresponds to an increase in the median from 24 to 40 weeks, with 80% power, a sample

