size of 84 patients (42/arm) is required, using a one-sided test at the $\alpha=0.10$ significance level. This assumes a two-year accrual period and a subsequent one-year follow-up period. Kaplan-Meier⁴¹ curves will be generated and the two treatment arms compared using a logrank test. Median time to event in each group will be estimated along with 90% confidence intervals using the method of Brookmeyer and Crowley⁴². Cox⁴³ proportional hazards regression models will be fit to assess and adjust for the effects of baseline covariates. Overall survival and radiographic progression-free survival will be analyzed similarly. The relative PSA change within each arm will also be reported using a waterfall plot according to working group recommendations for phase II studies in CRPC, as a secondary endpoint⁴⁴. Adverse events will be summarized by grade and type and compared between groups using chi-square or Fisher's exact tests.

For the secondary endocrine PD endpoint, we will compare endocrine PD marker differences between the enzalutamide alone versus the Enzalutamide + Mif treatment arms. In previous placebo controlled trials of Mif, serum cortisol levels reliably doubled from a baseline of approximately 15 $\mu\text{g}/\text{dL}$ to $>30 \mu\text{g}/\text{dL}$ after treatment with mifepristone^{38,39}. Based on the reported interquartile ranges, and assuming normality of the distribution, the coefficient of variation is estimated at 50%. An interim futility analysis will be conducted after half (35) of the expected 70 PSA events are observed. At this stage we will conduct an interim analysis of the difference in cortisol levels; a lack of biomarker effect would provide justification for closing the trial. Thus, assuming a true mean for the control arm of 15 and standard deviation of 7.5 on day 29 post randomization, our sample size will provide 90% power to detect a difference of 15 vs. 22 $\mu\text{g}/\text{dL}$ between the two treatment arms, based on t-test at a two-sided alpha level of 0.05. This calculation allows for a 15% missing data rate prior to day 29 post randomization. The other endocrine laboratories collected at day 29, will be similarly compared between treatment groups.

In addition, if at the interim analysis the conditional power for the primary PSA endpoint is $<25\%$, we will consider terminating the trial for futility. This stopping rule will provide minimal power loss ($<3\%$)⁴⁴.

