13.2 Randomization

Upon documented and confirmed eligibility, the patient will be enrolled and randomized. Randomization for phase II portions of the study will be done through [name] and colleagues in the biostatistics core at the University of Chicago in a 1:1 fashion. There will be no specific stratification as the 12-week standard of care enzalutamide lead in for the phase II study we hypothesize will add homogeneity to the population. As only patients with stable disease or better at 12 weeks are randomized any affect of prior therapy, etc. on the study population will be mitigated.

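### The primary PSA-PFS comparison is an unadjusted log-rank in an unstratified 84-patient trial, and the planned Cox adjustment has no named covariates and no stated role, although suitable baseline data are collected

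*Combined protocol and SAP*

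**What the plan says.** - **Primary comparison (13.1).** PSA progression-free survival after randomisation is compared by a log-rank test, "using a one-sided test at the $\alpha=0.10$ significance level". The section states that a "size of 84 patients (42/arm) is required" for 80% power at a hazard ratio of 0.60, and it expects 70 PSA events. No strata or covariates are attached to the test.
- **Adjustment (13.1).** Cox "proportional hazards regression models will be fit to assess and adjust for the effects of baseline covariates". No covariate is named, and the role of these models is not stated.
- **Randomisation (13.2).** "There will be no specific stratification as the 12-week standard of care enzalutamide lead in for the phase II study" is hypothesised to make the population homogeneous. The section adds that restricting entry to stable disease or better will mitigate any effect of prior therapy.
- **Secondary PFS (13.3).** A stratified log-rank is specified, but no strata are defined anywhere.
- **Data available.** Section 3.1 requires, for phase II entry, a "Record of subject's enzalutamide start date and baseline PSA" taken before enzalutamide. Sections 7.1 and 7.2 collect a screening PSA and a day 1 PSA. Section 4.1 records the dates and types of prior systemic therapy.
- **Interim (13.1).** At 35 events, conditional power below 25% for the primary endpoint leads to consideration of stopping.

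**The concern.** Two things are at stake.

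The first is efficiency. In a proportional hazards setting, leaving out a prognostic baseline factor pulls the estimated hazard ratio towards 1 and costs power relative to the adjusted test, even when the arms are perfectly balanced. The trial has 42 patients per arm and no stratification, so baseline information enters the primary test in no way at all. The argument in 13.2 that the lead-in makes patients alike is a hypothesis. Section 3.1 only requires PSA to be at most 1.25 times its starting value, so entrants can range from a 25% rise to a deep decline. Prior chemotherapy is neither required nor excluded.

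The second is prespecification. With the Cox covariates left open, several adjusted results are possible, and nothing says how a disagreement between them and the log-rank would be resolved.

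**Working it through.** **1. The plan's own figure.** Inputs from 13.1 and 13.2: hazard ratio 0.60, one-sided alpha 0.10, power 80%, 1:1 allocation, medians 24 and 40 weeks, two years of accrual plus one year of follow-up.

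Schoenfeld events: d = 4(z₀.₉₀ + z₀.₈₀)² / (ln 0.60)² = 4(1.2816 + 0.8416)² / 0.2609 = 69.1, so 70. This matches the plan's 70. Power at 70 events: Φ(0.5108 × √70 / 2 − 1.2816) = Φ(0.855) = 80.4%.

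With exponential survival and uniform accrual, the event probabilities in weeks are 0.930 and 0.812, mean 0.871, giving 84 × 0.871 = 73.1 expected events. In months (medians 6 and 10) they are 0.916 and 0.788, mean 0.852, giving 71.5. Power is 81-82%. The design reproduces for an unadjusted log-rank at hazard ratio 0.60.

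**2. One prespecified covariate.** Simulation of 84 patients, control median held at 24 weeks, 104 weeks of accrual and 52 of follow-up, one-sided 0.10, 4,000 trials per setting (Monte Carlo SE about 0.6 point for power and 0.5 for type I error). Prognostic strength is assumed, because the documents give none. Log-hazard SD is ln(HR per SD).

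| HR per SD (log-hazard SD) | 0.60 conditional: log-rank / adjusted | 0.60 marginal: log-rank / adjusted |
|---|---|---|
| 1.0 (0) | 80.2 / 79.8% | 80.2 / 79.8% |
| 1.25 (0.22) | 78.9 / 80.6% | 81.5 / 83.1% |
| 1.5 (0.41) | 75.4 / 80.2% | 80.1 / 84.8% |
| 1.75 (0.56) | 70.0 / 80.1% | 79.9 / 88.2% |
| 2.0 (0.69) | 67.5 / 79.6% | 79.8 / 90.7% |

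The gain is −0.4 point with no prognostic value, then about 2, 5, 8-10 and 11-12 points. Type I error was 10.0-10.8% adjusted and 10.1-10.7% for the log-rank.

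**3. Three covariates.** Two continuous and one binary with 40% prevalence, conditional hazard ratio 0.60, 3,000 trials per case.

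| Log-HR (per SD, per SD, binary) | Power: log-rank / adjusted | Type I error: log-rank / adjusted | Type I error if the most favourable of 8 covariate subsets is reported |
|---|---|---|---|
| 0, 0, 0 | 81 / 80% | 10.7 / 11.1% | 13% |
| 0.3, 0.2, 0.2 | 77 / 80% | 9.8 / 10.3% | 16% |
| 0.4, 0.3, 0.3 | 72 / 79% | 9.5 / 10.1% | 18% |
| 0.5, 0.4, 0.4 | 67 / 79% | 10.3 / 11.3% | 21% |

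The last column is a worst case. It would apply only if the covariate set were chosen after seeing results and the adjusted result then treated as decisive. With four adjustment terms, type I error reached 11.7-11.8%, against 10.0-10.2% for the log-rank, so the list should stay short.

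**4. Chance imbalance.** For a factor present in 40% of patients, with 42 per arm, the exact binomial probability that the arms differ by 15 points or more is 14.7%.

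**The case against.** The strongest reply is that an unadjusted log-rank after 1:1 randomisation is valid. Its type I error is at its nominal level, and that error rate already covers chance imbalance. The sample size was built for this test, and adjustment is already planned as a further analysis. All of this stands. The point concerns a more efficient primary test and an unspecified secondary one, not an invalid test.

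A reader might go further and infer that the trial loses power as planned and that adjustment would recover it at no cost. The documents do not support that, for four reasons.

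- **Prognostic value is not documented.** Nothing states or quantifies that these PSA values or prior chemotherapy predict PSA-PFS after week 12. The lead-in and the 1.25 limit may narrow their spread. At zero strength there is no gain.
- **Power is lost only on one reading of 0.60.** If it is the within-patient (conditional) effect, the log-rank falls below 80%. If it is the marginal effect that the log-rank tests, the log-rank has its 80% and adjustment adds to it. The 24 and 40 week medians do not settle which.
- **There is a cost.** The target becomes a conditional hazard ratio: about 0.57 when the marginal one is 0.60 and HR per SD is 1.5. The futility rule would be applied to a model with up to four terms at 35 events, about 9 events per term (35/4).
- **Timing of the PSA value.** Section 5.3 registers and randomises within the first 12 weeks of enzalutamide, while study treatment starts after week 12 and up to week 14. The day 1 PSA may therefore follow randomisation. PSA at randomisation is also the reference value in the progression definition, so its relation to the endpoint needs thought when the form is chosen.

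**Conclusion.** The point holds as a recommendation that should be acted on. The primary test ignores baseline data that the trial already collects, and the adjusted analysis that would use them is not specified.

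Over the assumed range, a prespecified adjusted test gains about 2 to 3 points of power for a weak score (log-hazard SD about 0.2-0.3), 5 to 8 for a moderate one (0.4-0.5) and up to about 12 for a strong one (0.7). The loss is about 1 point or less if nothing is prognostic. Type I error is about 10-11% with one to three covariates. These figures assume proportional hazards, exponential baseline survival and a correctly specified covariate form. The direction does not depend on whether 0.60 is conditional or marginal; only the starting level of the log-rank does.

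The prespecification gap, and the mismatch between 13.2 and 13.3, hold whatever the prognostic strength.

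**What to change.** Before any comparison by arm, write into 13.1:

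1. The primary test is the one-sided 0.10 test of treatment (state score or Wald) in a Cox model with two or three fixed covariates: log of the last PSA taken before randomised treatment starts; log ratio of that PSA to the pre-enzalutamide PSA; and, if wanted, prior chemotherapy (yes/no). Add no further terms.
2. The unadjusted log-rank is a sensitivity analysis.
3. The 35-event conditional-power rule uses the same statistic as the primary test, and the stated power loss of under 3% is re-checked for it.
4. The reported hazard ratio is labelled as conditional on the named covariates.
5. The stratified log-rank in 13.3 is reconciled with 13.2: either define its strata or drop the word.

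If the sponsor prefers to keep the log-rank primary, naming the covariates and calling the Cox models supportive still closes the selection problem.

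The cost is a text change plus a recheck of the futility rule. No new data are needed. The trade-off is a conditional target and a short covariate list that cannot be revisited.

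### The interim cortisol comparison that can justify closing the trial names only an unadjusted Day 29 t-test, although Day 1 cortisol is already drawn; a baseline-adjusted analysis judged by its confidence interval would be nearly free

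*Combined protocol and SAP*

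**What the plan says.** Section 13.1 (Sample Size/Primary Endpoint) introduces the endocrine endpoint with "we will compare endocrine PD marker differences between the enzalutamide alone versus the Enzalutamide + Mif treatment arms". An interim is set at 35 of the 70 expected PSA events, where "At this stage we will conduct an interim analysis of the difference in cortisol levels"; the text adds that "a lack of biomarker effect would provide justification for closing the trial".

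The sizing sentence follows. It works from "assuming a true mean for the control arm of 15 and standard deviation of 7.5 on day 29 post randomization" and says "our sample size will provide 90% power to detect a difference of 15 vs. 22" µg/dL, the contrast being made "between the two treatment arms, based on t-test at a two-sided alpha level of 0.05", with an allowance of 15% missing by Day 29. Just before this, "the coefficient of variation is estimated at 50" percent. Other Day 29 endocrine tests are to be handled in the same way.

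The same interim has a numerical rule for the primary endpoint: termination is considered "if at the interim analysis the conditional power for the primary PSA endpoint is" below 25%. No number accompanies the cortisol criterion.

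Section 7.2 and footnote k of the Study Calendar (Section 8.0) schedule cortisol and TSH on Days 1, 29 and 57. Section 13.1 mentions baseline covariates only for the Cox models.

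**The concern.** A comparison that can help close a trial should use the information already collected and should have a stated reading. Here there are three gaps.

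- **Baseline.** Day 1 cortisol is available in both arms, but the only named method ignores it. If Day 1 and Day 29 values are correlated, the t-test carries between-patient variation that could be removed at no cost in data.
- **Criterion.** Lack of biomarker effect is not defined. Without a definition, a non-significant t-test could be read as no effect, which is a different statement.
- **Basis of the 90%.** The SD is given alongside the control mean, none is given separately for the mifepristone arm, and it is not said whether the figure describes the interim or all 84 patients. A reader cannot tell how informative a null interim result would be.

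At stake is a decision to close on cortisol when mifepristone has a modest real effect on it.

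**Working it through.** **Inputs from the documents.** 84 patients, 42 per arm, 1:1; two-year accrual; PSA-PFS medians 24 and 40 weeks (HR 0.60); interim at 35 events; 15% missing; control mean 15, SD 7.5; alternative mean 22; CV 50%; two-sided 0.05.

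**Assumptions (ours).** Uniform accrual over 104 weeks; exponential event times; SD 11 (0.5 × 22) as one possible mifepristone-arm SD; Day 1 to Day 29 correlations of 0, 0.3 and 0.5.

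**1. Evaluable patients at the interim.** Expected events per arm by week t are (42/104) × [t − (1 − e^(−ht))/h], with h = ln 2/24 = 0.0289 for control and 0.6 × 0.0289 = 0.0173 under HR 0.60.

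- HR 0.60: at t = 80.7 the arms contribute about 20.0 + 15.0 = 35 events. Past Day 29: 84 × (80.7 − 4)/104 ≈ 61.9. Evaluable per arm: 61.9 × 0.85/2 = 26.3.
- HR 1: t = 73.9; past Day 29: 56.4; evaluable per arm: 24.0.

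Accrual over 52 or 156 weeks instead would give roughly 21 to 33 per arm. At full enrolment it is 42 × 0.85 = 35.7.

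**2. The plan's 90%.** SE = √[(7.5² + s²)/n], noncentrality = 7/SE, power from the noncentral t distribution (Welch degrees of freedom when the SDs differ).

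| Evaluable per arm | s = 7.5: SE, 7/SE, power | s = 11: SE, 7/SE, power |
|---|---|---|
| 24.0 (interim, HR 1) | 2.165, 3.23, 88.6% | 2.718, 2.58, 71.0% |
| 26.3 (interim, HR 0.60) | 2.068, 3.39, 91.3% | 2.596, 2.70, 75.1% |
| 35.7 (all 84) | 1.775, 3.94, 97.3% | 2.228, 3.14, 87.1% |

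The stated 90% is matched at the interim with a common SD of 7.5, and approached at full enrolment with SDs of 7.5 and 11.

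**3. Adding the Day 1 value.** ANCOVA multiplies the residual variance by about 1 − ρ², at the price of one degree of freedom. At 26 per arm with common SD 7.5, the SE goes from 2.080 (ρ = 0) to 2.080 × √0.91 = 1.984 (ρ = 0.3) and 2.080 × √0.75 = 1.801 (ρ = 0.5). Power for 15 vs 22, by simulation:

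| Scale | t-test | ρ = 0 | ρ = 0.3 | ρ = 0.5 |
|---|---|---|---|---|
| Raw, common SD 7.5 | 91% | 90% | 93% | 97% |
| Log, CV 50% in both arms | 82% | 81% | 85% | 90–91% |

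The log-scale row uses SD √(ln 1.25) = 0.472 and effect ln(22/15) = 0.383. It assumes log-normal data, whereas the plan assumes normality.

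**4. Reading a null result.** At 26 per arm with common SD 7.5, the 95% interval has half-width 2.009 × 2.080 = 4.18. An observed difference between −4.18 and 4.18 is non-significant. An upper limit below the plan's own 7 µg/dL requires an observed difference below 7 − 4.18 = 2.82. Between 2.82 and 4.18 the result meets neither condition.

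- No effect: non-significant in 95% of trials; upper limit below 7 in 91%.
- True difference 3: upper limit below 7 in 47% (40% with CV 50% in both arms).
- True difference 7: non-significant in 9% (SD 7.5 in both arms) or 25% (SDs 7.5 and 11); upper limit below 7 in 2.5%.
- True difference 15: upper limit below 7 in essentially no trials.

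With no effect, the inconclusive zone has probability Φ(4.18/2.08) − Φ(2.82/2.08) ≈ 0.98 − 0.91, or about 7%.

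**5. The expected effect.** The plan expects cortisol to double, to above 30. With mean 30 and SD 15 (CV 50%), SE = √[(7.5² + 15²)/26] = 3.29, noncentrality = 15/3.29 = 4.56, and power is about 99%.

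**The case against.** The defence is substantial. An unadjusted t-test between randomized arms is valid. The gain from a baseline term rests on a correlation that no document gives, is nil when that correlation is zero, and then costs about a point of power. The analysis wording refers to differences in markers and does not exclude a baseline term; the t-test appears only in the sizing text. A standard two-sample t-test uses one SD, and the plan supplies one. The closure sentence leads directly into the t-test, so the intended test can be inferred. Closure is discretionary, and a doubling of cortisol would hardly be missed. All of this stands and limits the point to a recommended improvement.

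What it does not answer is that Day 1 values are drawn and no planned use of them is stated for this comparison. Nor does high power at the expected effect supply a criterion. The PSA rule is also discretionary, yet it has a number.

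A reader might infer three stronger things. One is that the 90% is wrong, or is claimed for the interim and falls short there. The text refers only to the sample size, without saying which, and the figure is reachable or nearly so under either reading with a different SD; SD 11 is our extrapolation of the CV. Another is that the plan adopts non-significance as its closing rule; it does not say so. The third is that ignoring baseline biases the comparison; under randomization it does not.

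**Conclusion.** The point holds as a low-cost improvement, to be considered, with moderate confidence. The plan names only an unadjusted Day 29 t-test for a comparison that can justify closure, while the baseline values needed for a more precise analysis are already scheduled.

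The raw-scale effect on power at 26 per arm runs from about one point lost (correlation 0) to about six gained (correlation 0.5). It is conditional on assumed correlations and on a projected interim size. The lack of a criterion and of a stated N and SD is secondary: it leaves a null result open to over-reading. The documents do not support a claim that the trial is likely to be closed wrongly. The 9–25% chance of non-significance applies to a rise of 7, less than half the rise the plan expects.

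**What to change.** In Section 13.1:

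1. Specify that Day 29 cortisol is analysed by ANCOVA on arm and Day 1 value, on the raw scale under the plan's normality assumption (log scale as an option), reporting the difference or ratio with its 95% confidence interval. Use the same model for TSH. The plan gives no TSH variability, so no gain is claimed there.
2. Define lack of biomarker effect from that interval and not from non-significance alone. One example is an upper 95% limit of the difference below 7 µg/dL. Record a result that is neither significant nor below this limit as not supporting closure on cortisol.
3. State which N and which mifepristone-arm SD or CV lie behind the 90%.

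**Cost.** No new samples, visits or patients; the change is to protocol text, since Section 13.1 is part of the protocol. ANCOVA uses one degree of freedom, about one point of power if the correlation is zero. Without baseline adjustment, the interval rule is met somewhat less often than non-significance when there is no effect (about 91% against 95%), and it leaves an inconclusive zone for small effects.
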